4.2 Prior and Concomitant Therapy

Concomitant medication includes all pharmaceutical agents, vitamins, nutritional supplements, and herbal medicines used by the subject with the exception of *Octagam 10%* or placebo. Details on medications taken within 1 week prior to Screening and any concomitant medications taken during the study must be recorded in the electronic Case Report Form (eCRF). This includes off-label use of any drugs, devices, or interventions that have been used to manage COVID-19. Use of antivirals

(eg, remdesivir), corticosteroids, chloroquine or hydroxychloroquine, antibiotics, anticoagulants, or antiplatelet agents is allowed and must be documented in eCRF.

The use of medications being administered as part of other experimental studies or the use of experimental non-IVIG products, COVID-19 convalescent plasma, or interferons are forbidden. Should a circumstance arise where it is considered to be in the best interests of a subject to administer such a product, the subject should not receive further study infusions (*Octagam 10%* or placebo) if these are still ongoing. The other medications administered should be documented as concomitant medications, and the subject should continue to be followed up per protocol.

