4. Proportion of subjects with severe progression defined as requiring ECMO, IMV and/or have died through Day 33
5. Length of time in ICU through Day 33
6. Mortality rate through Day 33

Length of hospitalization is defined as (date of discharge – randomization date + 1). Subjects who are still hospitalized as of Day 33, subjects with missing end dates due

to withdrawal, subjects with unusable end dates due to prohibited medication use, or those who died on/prior to Day 33 will be censored at Day 33. The median time to discharge and associated 95% CI for each treatment arm will be estimated using the Kaplan-Meier method. Comparisons between treatment arms will be performed using a log-rank test, stratified by age category. A rate ratio and associated 95% CI, equivalent to a hazard ratio from a Cox proportional hazard model stratified by age, will also be presented.

Proportion of subjects that stabilized or improved at Day 14 is defined analogously to the primary endpoint and hypothesis testing for proportions will be conducted as described for the primary endpoint.

Cumulative duration on IMV through Day 33 is defined as (IMV end date - IMV start date + 1). Subjects who do not require IMV will have a duration set to 0. Subjects who die on or prior to Day 33 or are still on IMV at Day 33, will have a duration set to their actual/projected Day 33 date for the IMV end date, so long as prohibited medication was not administered. If IMV end date is missing but subject is discharged from ICU or hospital, then IMV end date will be set to the earlier of the ICU or hospital discharge date. Otherwise, subjects without usable IMV end date information due to withdrawal or prohibited medication use will use a projected Day 33 date for the IMV end date. Comparisons between treatment arms will be performed using a stratified Wilcoxon-Mann-Whitney (van Elteren) test with age category as a stratification factor.

Proportion of subjects with severe progression will be defined as the proportion that require ECMO, IMV, or died prior to Day 33. For this analysis, subjects who use prohibited medication prior to the earliest date of progression or Day 33 will not be included in analyses. Hypothesis testing for this endpoint will be conducted as described for the primary analysis.

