Length of time in ICU includes number of days spent in the ICU from randomization through Day 33 and is defined as [ICU discharge date - (later of ICU admittance date, randomization date) + 1]. Subjects who are not admitted to the ICU will have a duration set to 0. Subjects who die on or prior to Day 33 or are still in the ICU at Day 33, will have a duration set to their actual/projected Day 33 date for the discharge date, so long as prohibited medication was not administered. If ICU discharge date is missing but subject is discharged from hospital, then ICU discharge date will be set to hospital discharge date. Otherwise, subjects without usable ICU end date information due to withdrawal or prohibited medication use will use a projected Day 33 date for the ICU end date. Comparisons between treatment arms will be performed using a stratified Wilcoxon-Mann-Whitney (van Elteren) test with age category and baseline ICU status (In ICU at baseline versus not in ICU at baseline) as stratification factors.

Mortality rate is defined as the proportion of subjects who have died on or prior to Day 33. For this analysis, subjects who use prohibited medication prior to the earliest of death or Day 33 will not be included in analyses. Hypothesis testing will be performed as described for the primary analysis.

Key secondary endpoints which demonstrate statistical significance will be analyzed by subgroups including sex (male/female), race, ethnicity, geographic region, and disease severity (according to the definitions in the eCRF). All key secondary endpoints will be analyzed by age using testing analogous (unstratified) testing methodology to the specified analyses. Sensitivity analyses, using all available data, regardless of prohibited medication usage, will be conducted where applicable.

Additional details for missing data handling for key secondary endpoints are described in Section 9.2.4.

A detailed SAP describing additional missing data handling, additional sensitivity and subgroup analyses, and further details with respect to testing for each endpoint will be compiled as a separate document.

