##### **4.1 Missing Data**

The latest patient status available prior to Day 7 will be used to determine clinical status in the absence of a clinical status assessment. If a death date is prior to Day 7, clinical status at Day 7 will be identified as a 6. Otherwise, if a subject's last status reflects that they were in the ICU and receiving ECMO and/or IMV, clinical status will be imputed as a 5. Otherwise, if a subject's last status reflects that they were in the ICU and not receiving ECMO and/or IMV, clinical status will be imputed as a 4. If the LOCF clinical status value for a patient is higher than these imputed values or if a subject status cannot be derived based on available information on ECMO, IMV, or ICU status, the last observation carried forward (LOCF)

will be used to impute patient values. Subjects with no post-baseline clinical status assessment, or prohibited medication use, on or prior to Day 7 will be imputed as failure.

An imputation analogous to the primary endpoint will be performed for the secondary endpoint of clinical status at Day 14.

For the secondary endpoint length of hospitalization, Subjects who are still hospitalized as of Day 33, subjects with missing end dates due to withdrawal, subjects with unusable end dates due to prohibited medication use, or those who died on/prior to Day 33 will be censored at Day 33. Discharge occurring on or after the start date of prohibited medication use will not be considered an event.

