## 6. Analysis Populations

In the definitions below, an Analysis Population refers to a particular set of participants. Additional censoring rules for analyses based on these populations are described in relevant sections of the SAP. The definition applies to analyses for scheduled IDMC meetings and final analysis.

- Screened Population – The Screened Population includes all subjects who are screened.
- Enrolled Population – The Enrolled Population includes all subjects who enrolled in the study.
- Intent-to-Treat (ITT) Population – The Intent-to-Treat Population includes all subjects who are randomized.; Analysis will be conducted according to the study arm in which subjects are randomized, regardless of randomization errors or protocol violations.
- Safety (SAF) Population – The Safety Population includes all subjects who are randomized and received any amount of IVIG or placebo. The analysis will be conducted according to the treatment which subjects actually received. This analysis population is a subset of the ITT population.
- Per-Protocol (PP) Population - The Per-Protocol Population includes subjects who receive at least 75% of the planned dose (3 completed infusions of IVIG or placebo) without major protocol deviations that would potentially interfere with the efficacy assessment. This will be determined in consultation with the Octapharma Study leadership during blinded data review. The criteria for exclusion of subjects from the PP Population will be determined and documented prior to scheduled unblinding. The analysis will be conducted according to the treatment which subjects actually received. This analysis population is a subset of the ITT population.

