#### 14. Analysis of Secondary Endpoints

The analyses for secondary endpoints will be based on the ITT Population. The hypothesis testing with p-value assessments for secondary endpoints at designated timepoints will be implemented for confirmatory purpose after statistical significance is claimed from the primary endpoint. The following secondary endpoints will be analyzed by hierarchical procedure in the order specified below with overall 2-sided type I error of 0.05:

1. Length of hospital stay (time to discharge) through Day 33
2. Proportion of subjects with maintenance or improvement by at least one category on the 6-point clinical status scale on Day 14.
3. Cumulative duration of IMV through Day 33
4. Proportion of subjects with severe progression defined as requiring ECMO, IMV and/or have died through Day 33
5. Length of time in ICU from randomization through Day 33
6. Mortality rate through Day 33

The hierarchical testing procedure will stop when one of the endpoints cannot demonstrate statistical significance, i.e. as soon as the first statistical test yields a p-value  $\geq 0.05$ . If this happens, the subsequent endpoints will not be tested.

Length of hospitalization is defined as (date of discharge – randomization date + 1). Subjects who are still hospitalized as of Day 33, subjects with missing end dates due to withdrawal, subjects with unusable end dates due to prohibited medication use, or those who died on/prior to Day 33 will be censored at Day 33. The median time to discharge and associated 95% CI for each treatment arm will be estimated using the Kaplan-Meier method. Comparisons between treatment arms will be performed using a log-rank test, stratified by age category. A rate ratio and associated 95% CI, equivalent to a hazard ratio from a Cox proportional hazard model stratified by age, will also be presented.

Proportion of subjects that stabilized or improved at Day 14 is defined as per the primary endpoint and hypothesis testing for proportions will be conducted as described for the in the primary endpoint section.

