Cumulative duration on IMV through Day 33 and is defined as (IMV end date – IMV start date + 1). Subjects who do not require IMV will have a duration set to 0. Subjects who die on or prior to Day 33 or are still on IMV at Day 33, will have a duration set to their actual/projected Day 33 date for the IMV end date, so long as prohibited medication was not administered. If IMV end date is missing but subject is discharged from ICU or hospital, then IMV end date will be set to the earlier of the ICU or hospital discharge date. Otherwise, subjects without usable IMV end date information due to withdrawal or prohibited medication use will use a projected Day 33 date for the IMV end date. Comparisons between

treatment arms will be performed using a stratified Wilcoxon-Mann-Whitney (van Elteren) test with age category as a stratification factor.

Proportion of subjects with severe progression will be defined as the proportion that require ECMO, IMV or died prior to Day 33. For this analysis, subjects who use prohibited medication prior to the earliest of progression or Day 33 will not be included in analyses. Hypothesis testing for this endpoint will be conducted as described for the primary endpoint.

Length of time in ICU from randomization through Day 33 includes number of days spent in the ICU from randomization through Day 33 and is defined as [ICU discharge date – (later of ICU admittance date, randomization date) + 1]. Subjects who are not admitted to the ICU will have a duration set to 0. Subjects who die on or prior to Day 33 or are still in the ICU at Day 33, will have a duration set to their actual/projected Day 33 date for the discharge date, so long as prohibited medication was not administered. If ICU discharge date is missing but subject is discharged from hospital, then ICU discharge date will be set to hospital discharge date. Otherwise, subjects without usable ICU end date information due to withdrawal or prohibited medication use will use a projected Day 33 date for the ICU end date. Comparisons between treatment arms will be performed using a stratified Wilcoxon-Mann-Whitney (van Elteren) test with age category and baseline ICU status (In ICU at baseline versus not in ICU at baseline) as stratification factors.

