Mortality rate is defined as the proportion of subjects who have died on or prior to Day 33. For this analysis, subjects who use prohibited medication prior to the earliest of death or Day 33 will not be included in analyses. Hypothesis testing will be performed as described for the primary endpoint.

Key secondary endpoints which demonstrate statistical significance will be analyzed by subgroups including sex (male/female), race, ethnicity, geographic region, and disease severity (according to the definitions in the eCRF). All key secondary endpoints will be analyzed by age using testing analogous (unstratified) testing methodology to the specified analyses. Length of time in ICU from randomization through Day 33 will also be analyzed by baseline ICU status. Sensitivity analyses, using all available data, regardless of prohibited medication usage, will be conducted where applicable. The descriptive analyses for the following other secondary endpoints will be based on the primary efficacy analysis (e.g. CMH) method:

- Proportion of patients whose results of reverse transcription polymerase chain reaction (RT-PCR) for SARS-CoV-2 from nares/throat swab and/or sputum and/or lower respiratory tract sample are “Not Detected” on Day 7
- Proportion of subjects admitted to the ICU from randomization through Day 33
  - Only admittance (new or returning) post-randomization will qualify as an event
  - Analyses will be stratified additionally by baseline ICU status
  - If expected event counts do not satisfy CMH testing criteria, baseline ICU status will be removed from analysis as a first step in analysis update
- Proportion of subjects with improvement on Days 7, 14, 21, 33

- Proportion of subjects requiring IMV by Day 33.

The descriptive analyses for the following, other secondary endpoints will be based on the Kaplan-Meier analysis of length of hospitalization:

- Time to recovery through Day 33 where recovery is defined as a clinical status of 1 or 2
- Time to first improvement in clinical status through Day 33

These secondary endpoints will also be analyzed by age category.

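### The confirmatory tests of severe progression and mortality drop randomised, still-followed subjects who used prohibited medication

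*SAP*

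**What the plan says.** SAP section 14 tests six key secondary endpoints in a fixed order at two-sided 0.05 once the primary endpoint is significant. Severe progression (ECMO, IMV or death) is fourth and mortality is sixth. The general statement is "The analyses for secondary endpoints will be based on the ITT Population". SAP section 6 defines that population as everyone randomised, adding "Analysis will be conducted according to the study arm in which subjects are randomized, regardless of randomization errors or protocol violations".

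Two endpoint-specific rules then remove subjects:

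- Severe progression: "subjects who use prohibited medication prior to the earliest of progression or Day 33 will not be included in analyses" (SAP section 14) and "subjects who use prohibited medication prior to the earliest date of progression or Day 33 will not be included in analyses" (Protocol section 9.2.3.2).
- Mortality: "For this analysis, subjects who use prohibited medication prior to the earliest of death or Day 33 will not be included in analyses" (SAP section 14) and "subjects who use prohibited medication prior to the earliest of death or Day 33 will not be included in analyses" (Protocol section 9.2.3.2).

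SAP section 13 lists the prohibited products as drugs given within other experimental studies, experimental non-IVIG products, convalescent plasma and interferons. Under Protocol section 4.2 a subject given one of these receives no further study infusions, but "the subject should continue to be followed up per protocol".

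Some planned analyses do keep these subjects. For severe progression, Protocol section 9.2.5 and SAP section 4.1 add one version that counts prohibited use as an event and one that ignores it. For the key secondaries in general, Protocol section 9.2.3.2 and SAP section 14 promise all-data sensitivity analyses where applicable. None of these is in the numbered hierarchy.

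**The concern.** Prohibited use is a post-randomisation event. Protocol section 4.2 foresees it when it is judged to be in the subject's best interests, so it is plausibly related to prognosis. If users are removed, the tested groups are no longer the groups that were randomised. If use also differs between arms, the comparison is biased:

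- More use on placebo removes more placebo deaths, which hides a benefit or suggests harm.
- More use on IVIG removes more IVIG deaths, which can create an apparent benefit.

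There is little reason to accept this for death, IMV and ECMO, because they remain observable after prohibited use and follow-up is required to continue. At stake is whether a confirmatory statement on the trial's two hardest endpoints rests on a randomised comparison.

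**Working it through.** **1. How the plan treats the same event across endpoints**

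| Endpoint | Subject with prohibited use |
|---|---|
| Primary, Day 7 status | Kept as failure ("or prohibited medication use, on or prior to Day 7 will be imputed as failure", SAP section 4.1; also section 13) |
| Key 1, time to discharge | Kept, censored at Day 33 |
| Key 2, Day 14 status | Kept as failure, by analogy with Day 7 |
| Key 3, IMV duration | Kept; if on IVM-type support with no usable end date, extrapolated to Day 33 |
| Key 4, severe progression | Removed if use precedes progression (or Day 33 if none) |
| Key 5, ICU time | Kept; if in ICU with no usable end date, extrapolated to Day 33 |
| Key 6, mortality | Removed if use precedes death (or Day 33 if alive) |

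Only the two endpoints that count deaths as events drop these subjects. Two consequences follow:

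- A subject who is intubated, then given a prohibited product, and then dies is an event in endpoint 4 but absent from endpoint 6.
- In endpoint 4 an early withdrawal with no recorded event stays in as a non-event (SAP section 4.1), while a user who is still followed is taken out.

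**2. Inputs for a size illustration (mortality)**

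- From the documents: 104 per arm and two-sided 0.05. The plan's sample size reproduces: 176/(1 − 0.15) = 207.1, so 208. At 88 per arm, 0.6 versus 0.8 gives 83.1% power, consistent with at least 80%. The plan gives no figure for mortality or severe progression.
- Assumed, because the documents give no values: overall mortality m, proportion of users u in each arm, and mortality among users q = 50%.
- Apparent mortality after exclusion: (m − u·q)/(1 − u).
- Test: unstratified pooled z-test, 400,000 simulated trials per scenario.

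**3. No true effect, m = 20% in both arms**

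For 10% use: (0.20 − 0.10×0.5)/0.90 = 16.7%. For 5%: (0.20 − 0.05×0.5)/0.95 = 18.4%. For 15%: (0.20 − 0.15×0.5)/0.85 = 14.7%.

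| Use, placebo / IVIG | Apparent mortality, placebo / IVIG | Two-sided error | False benefit | False harm |
|---|---|---|---|---|
| 5% / 5% | 18.4% / 18.4% | 5.0% | 2.5% | 2.5% |
| 10% / 5% | 16.7% / 18.4% | 6.2% | 1.2% | 5.0% |
| 15% / 5% | 14.7% / 18.4% | 10.3% | 0.4% | 9.9% |
| 5% / 10% | 18.4% / 16.7% | 6.2% | 5.0% | 1.2% |
| 5% / 15% | 18.4% / 14.7% | 10.3% | 9.9% | 0.4% |

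At 10% use an arm loses 104×0.10×0.5 = 5.2 of its 104×0.20 = 20.8 expected deaths. At 15% it loses 7.8. An exact calculation with user numbers fixed at their expected values gives 10.7% at 15% versus 5%. An age-stratified CMH version (200,000 trials; assumed 30% of subjects over 65, with twice the mortality of the younger stratum) gives 5.0%, 6.1% and 10.3% for the first three rows.

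**4. True mortality 25% placebo, 15% IVIG**

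| Use, placebo / IVIG | Apparent mortality, placebo / IVIG | Difference (points) | Power |
|---|---|---|---|
| All randomised kept | 25.0% / 15.0% | 10.0 | 44% |
| 10% / 5% | 22.2% / 13.2% | 9.1 | 38% |
| 15% / 5% | 20.6% / 13.2% | 7.4 | 28% |
| 5% / 10% | 23.7% / 11.1% | 12.6 (overstated) | 64% |

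**5. How far the assumptions drive this**

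Two-sided error with no true effect:

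- User mortality 30%, overall 20%: 5.1–5.2% at 10% versus 5% use, and 5.5% when IVIG use is 15% and placebo use 5%.
- User mortality 50%, overall 20%, rarer use: about 5.2% at 4% versus 2%, and 5.3–5.4% at 5% versus 2%.
- User mortality 50%, overall 15% (exact): 7.1% at 10% versus 5%, and 15.7% at 15% versus 5%.
- User mortality 50%, overall 10% (exact): 9.4% at 10% versus 5%, and 33.4% at 15% versus 5%. The last case is extreme, because users would account for 7.8 of the 10.4 expected deaths in the higher-use arm.

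**The case against.** The strongest defence has four parts.

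- **Prespecified and disclosed.** The rule is the same in both documents, SAP section 6 warns of additional censoring rules, and SAP section 12 defers handling after prohibited use to the analysis sections. This is correct, so there is no conflict between protocol and SAP. Disclosure does not restore the randomised comparison.
- **The deaths are still reported.** SAP section 10 tabulates clinical status, including death, for the ITT population regardless of prohibited use. SAP section 16 tabulates adverse events leading to death by arm, and all-data sensitivity analyses are planned. This also stands, and a reader of the report could see the discrepancy. The confirmatory p-value would still come from the reduced set. For mortality alone, the commitment rests clearly only on the general sentence about sensitivity analyses.
- **Use may be rare and balanced.** The prohibited list is narrow, remdesivir and corticosteroids are allowed, planned use of plasma or interferons is an exclusion criterion, and the trial is double-blind. Nothing in the documents supports 15% use or a threefold imbalance. With equal use and no true effect the error stays at 5%. This limits the likely size, though lower overall mortality pushes it the other way.
- **The tests are gated.** Mortality is reached only after the primary and five key secondaries succeed, and severe progression after the primary and three. The error rates above are for a stand-alone test, not conditioned on that gate, so they are upper bounds on the chance of a false claim in the trial.

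In addition, Protocol section 4.3.1 allows participation to end for non-compliance, so Day 33 status may not be complete for every user.

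**Conclusion.** The concern holds. Two confirmatory tests that are described as ITT remove randomised subjects on a post-randomisation event, although their outcomes should be known and the other key endpoints retain them. This conclusion comes from the text and does not depend on the simulations.

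The size is undetermined. With 20% overall mortality and 50% mortality in users, two-sided error runs from 5.0% (equal use) to about 10% (15% versus 5% use). It is barely above 5% if users' mortality is nearer the overall rate or use is rare, and larger if overall mortality is lower. False benefit requires more use on IVIG; more use on placebo costs power or suggests harm. The effect is confined to gated endpoints 4 and 6, and the primary endpoint is untouched. It should be fixed, but it does not threaten the main result.

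**What to change.** In SAP section 14 and Protocol section 9.2.3.2:

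- Make the confirmatory analysis of severe progression and of mortality use all randomised subjects, with observed death, IMV and ECMO status through Day 33 regardless of prohibited medication.
- Move the exclusion version of each to a sensitivity analysis outside the hierarchy.
- Name mortality explicitly among the endpoints with an analysis regardless of prohibited use, and state how missing Day 33 status is handled. The withdrawal rule in SAP section 4.1 is written for severe progression.

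The cost is a SAP revision and a protocol amendment with its usual agreement and submission, completed before unblinding. No new patients or assessments are needed: follow-up after prohibited use is already required, and the all-data analysis is already planned for severe progression and, where applicable, for the other key secondaries. The change mainly exchanges the roles of two analyses.

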2.2 Secondary Objectives

Key Secondary Efficacy Objectives

- To compare the length of hospital stay in subjects treated with *Octagam 10%* compared to those that received placebo through Day 33.
- To determine if high-dose *Octagam 10%* therapy will stabilize or improve clinical status in subjects with severe COVID-19 during the 14 days following treatment commencement.
- To compare the cumulative duration of invasive mechanical ventilation (IMV) in subjects treated with *Octagam 10%* compared to those that received placebo through Day 33.
- To compare the cumulative incidence of severe progression in subjects treated with *Octagam 10%* compared to those that received placebo at Day 33.
- To compare the length of time in ICU in subjects treated with *Octagam 10%* compared to those that received placebo at Day 33.
- To compare cumulative mortality in subjects treated with *Octagam 10%* compared to those that received placebo at Day 33.

Other Secondary Efficacy Objectives

- To determine if high-dose *Octagam 10%* affects severe acute respiratory syndrome from Coronavirus 2 (SARS-CoV-2) infection status at Day 7.
- To compare the cumulative incidence of new ICU admittance in subjects treated with *Octagam 10%* compared to those that received placebo at Day 33.
- To determine if high-dose *Octagam 10%* therapy will improve clinical status in subjects with severe COVID-19 during the 14 days following treatment commencement.
- To compare the cumulative incidence of IMV in subjects treated with *Octagam 10%* compared to those that received placebo through Day 33.
- To compare the time to recovery in subjects treated with *Octagam 10%* compared to those that received placebo through Day 33.

- To compare the time to first improvement in clinical status in subjects treated with *Octagam 10%* compared to those that received placebo through Day 33.

Secondary Safety Objective

- To describe the safety of *Octagam 10%* compared to placebo when administered to subjects with severe COVID-19.

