3.1.2.2 Other Secondary Efficacy Endpoints

- Results of reverse transcription polymerase chain reaction (RT-PCR) for SARS-CoV-2 from nares/throat swab and/or sputum and/or lower respiratory tract sample on Day 7.
- Proportion of subjects admitted to the ICU from randomization through Day 33
- Proportion of subjects with improvement on Days 7, 14, 21, and 33
- Proportion of subjects requiring IMV by Day 33
- Time to recovery through Day 33 where recovery is defined as a clinical status of 1 or 2
- Time to first improvement in clinical status through Day 33

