### **Proportion of subjects admitted to the ICU from randomization through Day 33**

This is defined as the proportion of subjects who were admitted to the ICU in the period from the date of randomization to Day 33. If a subject has two or more events during this time, (s)he will still be counted only once.

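### The ICU-admission endpoint keeps subjects already in ICU at baseline and counts their readmissions, so for them it does not measure the new-admission objective

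*SAP*

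**What the plan says.** Protocol 2.2 lists this among the other secondary objectives: "To compare the cumulative incidence of new ICU admittance in subjects treated with" Octagam 10% against placebo, at Day 33. The matching endpoint in Protocol 3.1.2.2 drops the qualifier: "Proportion of subjects admitted to the ICU from randomization through Day 33". SAP 2.2.1 repeats the endpoint in that form, and SAP 12 defines it as "the proportion of subjects who were admitted to the ICU in the period from the date of randomization to Day 33", each subject counted once. The SAP's own list of other secondary objectives leaves this one out, although SAP 20 reports no change from the protocol.

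SAP 14 sets the analysis. On the population: "The analyses for secondary endpoints will be based on the ITT Population", and SAP 6 defines that set: "The Intent-to-Treat Population includes all subjects who are randomized". On the event: "Only admittance (new or returning) post-randomization will qualify as an event". On adjustment, beyond age: "Analyses will be stratified additionally by baseline ICU status". There is also a fallback: "If expected event counts do not satisfy CMH testing criteria, baseline ICU status will be removed from analysis as a first step".

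Subjects in ICU at baseline are expected. Clinical status category 4 includes ICU care, Protocol 4.1.2 excludes recent or current invasive ventilation but not ICU residence, and SAP 14 names being in ICU at baseline as a stratum. No rule for this endpoint makes a continuing ICU stay or a death an event, or treats death as a competing event.

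**The concern.** A subject already in ICU cannot have a new ICU admission. Keeping such subjects in the denominator and counting returns replaces the objective's event with one that can occur only after the subject has improved enough to leave. The worst course (never leaving, or dying in ICU) and the best course (leaving for good) get the same score, and the only course that counts against a treatment lies between them.

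What is at stake is the reading of one reported difference and its confidence interval. It would be labelled ICU admission but would mix new admissions among subjects at risk with readmissions among subjects who were not. The mix dilutes any effect on new admission and can move the estimate against an arm that gets more subjects out of ICU.

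**Working it through.** The plan gives no rate, event count or power for this endpoint, so there is no stated figure to reproduce. The arm size of 104 is from Protocol 9.1. Every rate below is an assumption.

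**Step 1. Score each course under the SAP rule.**
- Not in ICU at baseline, later admitted: event, whatever follows.
- Not in ICU at baseline, never admitted, alive or dead: non-event.
- In ICU at baseline, leaves and does not return: non-event.
- In ICU at baseline, leaves and returns: event.
- In ICU at baseline, never leaves, or dies there: non-event.

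**Step 2. Event probability for a baseline-ICU subject.** P(event) = P(leaves ICU) × P(returns, given left).

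Assume 20 baseline-ICU subjects per arm, 8 leaving on placebo and 14 on Octagam, and 15% of leavers returning in both arms.
- Placebo: 8 × 0.15 = 1.2 events (6.0% of 20).
- Octagam: 14 × 0.15 = 2.1 events (10.5% of 20).
- Difference: 0.9 events, and 0.9/104 = about 0.9 points on the whole arm.
- Break-even: the reversal disappears if return among Octagam leavers is no higher than 1.2/14 = 8.6%.

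**Step 3. Effect on the stratified estimate.** Let s be the baseline-ICU share, equal in both arms. The Mantel-Haenszel risk difference is then s × (difference in the ICU stratum) + (1 − s) × (difference in the other stratum). Assume 50% (placebo) versus 80% (Octagam) leave ICU and a proportion r of leavers return in both arms, so the ICU-stratum difference is 0.30 × r. Take s from 10% to 40% and r from 10% to 25%.
- No true effect on new admission (20% in both arms). Smallest: 0.10 × 0.30 × 0.10 = +0.3 points. Largest: 0.40 × 0.30 × 0.25 = +3.0 points. Both go against the arm that empties ICU faster. Restricting to subjects not in ICU at baseline gives 0.
- True benefit of 5.0 points (20% versus 15%). Smallest distortion: 0.90 × (−5.0) + 0.3 = −4.2 points. Largest: 0.60 × (−5.0) + 3.0 = 0.0 points. The restricted analysis gives −5.0.

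Stratification balances the mix of subjects between arms, but the reversal arises inside the baseline-ICU stratum and is averaged into the common estimate.

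**Step 4. Would the fallback be reached?** The only CMH criterion the SAP names is Mantel-Fleiss (SAP 13), which sums over strata. Its usual threshold is 5, a figure the SAP does not print. With equal arms and these event rates, the criterion equals the expected events in one arm. Use 20% for subjects not in ICU and 6.5% for those in ICU, the mean of 0.50 × 0.10 = 5.0% and 0.80 × 0.10 = 8.0%.
- s = 10%: 104 × (0.10 × 0.065 + 0.90 × 0.20) = 19.4.
- s = 40%: 104 × (0.40 × 0.065 + 0.60 × 0.20) = 15.2.

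Both are well above 5, so the stratum would be kept.

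**The case against.** The strongest reply is that little depends on this endpoint. SAP 14 calls its analysis descriptive, it lies outside the six-step hierarchy, and it supports no success claim. Poor outcomes of baseline-ICU subjects are not hidden either. Length of time in ICU extends deaths to Day 33, is stratified by baseline ICU status and is also analysed by it. Death counts again in severe progression and in mortality. All of this stands, and it limits the severity. It does not make the reported proportion an estimate of the stated objective.

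It is also fair to say that the mismatch starts in the protocol, between its objective and its endpoint, and that the SAP follows the endpoint.

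Three stronger readings are tempting and are not supported:
- A reader might infer that the endpoint always runs opposite to benefit among baseline-ICU subjects. That depends on readmission. In Step 2 it reverses only while return among Octagam leavers stays above 8.6%.
- A reader might infer that the fallback favours whichever arm has more baseline-ICU subjects. The fallback needs the CMH criteria to fail, which they do not at the event counts in Step 4. An unequal split between randomized arms would be chance imbalance, not a bias built into the plan.
- A reader might infer that an ICU death generally scores as a good outcome here. That is so only for subjects in ICU at baseline who never left. For anyone else the first admission is already an event.

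**Conclusion.** The point holds as a mismatch between objective and endpoint, confined to subjects in ICU at baseline. For them the event requires leaving ICU first, and an uninterrupted stay or death in ICU is a non-event. A treatment that frees more subjects from ICU can therefore raise the proportion unless it lowers readmission enough, and the planned stratification does not remove this.

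The structural finding rests on the text alone. The size does not. It is about 0.9 points in the single illustration and 0.3 to 3.0 points over the assumed range, and it depends on three quantities the documents do not give. Because the endpoint is descriptive and ICU stay and death are measured elsewhere, severity is low to moderate.

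**What to change.** In SAP 12 and 14, and in the matching protocol endpoint wording:
- Define the endpoint as first ICU admission from randomization through Day 33 among ITT subjects not in ICU at baseline, stratified by age. Baseline ICU status is already used in the analysis, and SAP 4 takes efficacy baseline before randomization, so the comparison remains a randomized one.
- State how death without ICU admission is handled, for example by also reporting ICU admission or death. Restricting the denominator does not by itself deal with a ward death.
- Report readmissions of baseline-ICU subjects separately and descriptively.
- Remove the baseline-ICU stratum and its fallback for this endpoint, as no longer needed.
- Restore the objective in SAP 2.2.

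The cost is a wording change and a smaller denominator for one descriptive endpoint. The subjects removed cannot have the event that the objective names.
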